M	
Primary Study Objective
 
To assess retrospectively the effect of NTRK gene fusions on the progression free survival (PFS) of first-line systemic therapy for the treatment of locally advanced/unresectable or metastatic solid tumors

O	
Secondary Study Objectives
 
 
• To evaluate the frequency of NTRK gene fusions in subjects with locally advanced/unresectable or metastatic solid tumors.
 
• To assess the treatment outcome to first-line anti-cancer therapy in terms of objective response rate (ORR), duration of response (DOR), and overall survival (OS) in subjects with locally advanced/unresectable or metastatic solid tumors with NTRK gene fusions.
 
• To explore possible demographic characteristics prevalent in subjects with locally advanced/unresectable or metastatic solid tumors and NTRK gene fusions.
 
• To explore the frequency and treatment outcome interaction of concomitant genetic alterations.
 
• To look for trends in the data that may suggest relationships between covariates of interest and treatment outcome in subjects with locally advanced/unresectable or metastatic solid tumors harboring NTRK gene fusions.
 

M	
Study operational/organizational aspects
 
This will be a multicenter, retrospective study. Institut Bergonié as the Sponsor of this study, will be responsible for getting regulatory approvals, selecting the investigational sites, capturing study data in an appropriate data base

Population and methods	
M	
Study Population
 
Adult and pediatric patients with locally advanced/unresectable or metastatic solid tumors

M	
Inclusion Criteria (detailed)
 
For inclusion of a subject in the study population, all of the following criteria must be fulfilled:
 
 
1. Age <math>\geq</math> 1 month.
 

2. Subject has/had a histologically or cytologically confirmed diagnosis of solid tumor including but not exclusively: soft tissue sarcoma, BRAF wild type melanoma, KRAS wild-type colorectal cancer, central nervous system, EGFR-wild type non-small cell lung cancer.

3. Subject has locally advanced/unresectable or metastatic disease.

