4. Subject has received at least one systemic anti-cancer therapy for locally advanced/unresectable or metastatic disease for which there is available outcome information in terms of PFS, or the latter can be estimated based on the subject's records.

5. Subject has tumor material available for immunoscreening (IHC for NTRK gene fusions).

6. Written and voluntary informed consent understood, signed and dated, or a waiver of consent is granted according to French regulations

Subjects who are tested positive by IHC (Pan-Trk IHC testing with mAb EPR17341) will be the subject of molecular assays such as next-generation sequencing (Archer Dx fusion assay) of tumor material [parrafin embedded material]), so that tumor harboring *NTRK1*, *NTRK2* or *NTRK3* gene fusions, is identified properly.

After identification of the NTRK fusion study population, control subjects with locally advanced/unresectable or metastatic solid tumors, who do not have NTRK fusions will be selected in an attempt to closely match NTRK fusion subjects.

M	
Exclusion Criteria
 
The following exclusion criterion should be considered:
 
Subjects who have not yet received or completed at least one systemic anti-cancer therapy for locally advanced/unresectable or metastatic cancer.

M	
Test Treatment(s) (Description)
 
n/a
 
.

O	
Test Treatment(s) or Investigated Treatment(s): Rationale for unusual or novel approaches
 
n/a

M	
Request for Study Drug Supply
 
No

M	
Reference Treatment or Modality/Treatment or Modality of Comparison (Description)

	n/a
--	-----

Safety reporting	
M	Safety reporting (valid for clinical studies only) n/a

Statistical analysis	
O/M	Standard of Reference/Standard of Truth n/a
M	Rationale for selection of a reference treatment n/a
M	Assignment of subjects to study arms or groups (Randomization/Stratification) n/a (this will be a retrospective study)
M	Blinding n/a
M	Concomitant Treatment(s) n/a
M	Primary Outcome Progression-free survival observed with first-line anti-cancer therapy

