O	Secondary Outcomes 
 
Frequency of NTRK fusions in subjects with locally advanced/unresectable or metastatic solid tumors.
 
Treatment outcome to first-line anti-cancer therapy in terms of objective response rate (ORR), duration of response (DOR), and overall survival (OS) in subjects with locally advanced/unresectable or metastatic HNSCC with NTRK gene fusions.
 
Demographic characteristics in subjects with locally advanced/unresectable or metastatic solid tumors harboring NTRK gene fusions
 

M	Safety Outcomes n/a
O	Measurement of results (How assessed)

	Data collection (see below)		
M	Visit schedule		
	Activity	Screening	Data Collection for Enrolled Subjects
	ICF, Inclusion/exclusion criteria evaluation	X	
	Collection of Demographic Information: 
 
• Date of birth
 
• Vital status: dead/alive/unknown
 
• Gender
 
• Smoking status: Smoker/never smoker/prior smoker at the time of first line treatment
 
• Other relevant carcinogen exposure (e.g. consumption of betel nut)
 
		X
	Collection of Medical Information: 
 
• Date of initial diagnosis of cancer
 
• Stage of disease at diagnosis
 
• Anatomical disease site(s) at diagnosis
 
• Anatomical (organ) disease site(s) (e.g. lung metastases) at the time of first line treatment
 
• Locally advanced/unresectable or metastatic disease at the time of first line treatment
 
• Current stage of disease
 
• Other relevant medical history. Date of prior medical events
 
		X

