	Collection of Treatment Information: 
 
• Prior/current surgical treatments for cancer. 
 
• Dates of surgeries
 
 
 
• Prior/current radiological treatments for cancer. 
 
• Anatomical sites.
 
• Dates of radiation treatments
 
 
 
• First line systemic treatment for locally advanced/unresectable or metastatic cancer: 
 
• Dates of treatment (start, end).
 
• Performance status at the time of first line therapy for treatment of recurrent or metastatic disease.
 
• Treatment outcome (response and response criteria).
 
• Date of progression(s) (progression criteria).
 
 
 
• Other prior/current systemic treatments for cancer. 
 
• Dates of treatment (start, end).
 
• Treatment outcome (response and response criteria).
 
 
 
• Date of progression(s) (progression
 
		X

	
criteria)
 
 
• Date of death (if any) and cause of death
 
 
Collection of NTRK fusion Information:
 
 
• Anatomical biopsy sample site (including blood/urine sample). Date of sampling and setting (initial diagnosis, locally advanced/unresectable or metastatic disease)
 
• Matrix (tumor biopsy, blood, urine)
 
• Tumor histology (from biopsy sample or primary diagnosis)
 
• NTRK fusion in sample. Allele frequency (if available); this information is not applicable for control subjects.
 
• Other relevant mutations or genetic alterations, if available. Allele frequencies (if available)
 
• Test platform (e.g. NGS). Mutations tested (PCR methods) or exons sequenced (sequencing methods).
 
		
			X
M	
Follow-up period
 
n/a
		

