M	
Statistical & Analytical Plan and Methodology
 
The primary objective of this descriptive study is to determine if there are statistically significant differences in PFS to first line systemic therapy between subjects with recurrent/metastatic disease and NTRK fusion versus those without a known NTRK fusion.
 
The two groups will be matched with respect to histological subtype, sex, age (+/-5 years), and pathological tumor-node-metastasis (TNM) stage.
 
The Kaplan-Meier method will be employed for the analysis of PFS. A nonparametric test, such as the log-rank test, based on the Kaplan-Meier estimator for survival curves, will be employed to assess the association between PFS and the presence of NTRK fusion. In addition, predictive modeling, including Cox proportional hazards models with NTRK fusion as a predictor may also be used to estimate the relative risk of the exit-event of subjects with tumors with NTRK fusion versus subjects with tumors without known NTRK fusion. If the data allow it, other types of predictive modeling may also be explored. If the proportionality of hazard assumption fails, then parametric approaches will be used.
		

	
Given the rarity of NTRK fusions among subjects with solid tumors, the sample size for this study will not be driven by powering the study. A post hoc power calculation will be provided. Clinically relevant changes will be defined as increases in median survival times that are greater than 30%, regardless of confidence interval width.
 
An assessment of the impact of certain covariates will be conducted by comparing their associated hazard ratios from the Cox proportional hazard (or parametric model) analysis.
 
Descriptive statistics will be employed to define demographic and treatment outcome, as well as overall frequency of NTRK fusions in the screened population. This will include exploration of potential effects on subject's treatment outcomes of different forms of NTRK fusions and of other genetic alterations.

--	--

Timelines	

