M	
Planned Study Timelines:
 
 
1. Enrolment rate (patients per month): 300 patients/months
 
2. Planned estimate of treatment duration: not applicable
 
3. Submission date to health authority/ethics: not applicable
 
4. Start of subject enrolment: December 2018
 
5. End of Subject enrolment: December 2019
 
6. All patients completed: December 2019
 
7. End of Study: March 2020
 
8. Report (as described in the contract): Report every 3 months
 
9. Planned publication/presentation: June 2020
 

Limitations	
O	
Criteria for selection of evaluable cases:
 
All patients:
 
who have received at least one systemic anti-cancer therapy for locally advanced/unresectable or metastatic disease for which there is available outcome information in terms of PFS,
 
who have tumor material tested by IHC for NTRK gene fusions,
 
will be included in the analysis.

M	Interim Analyses (if applicable)

	
Interim analyses will be the subject of periodic reports based upon collection of data on first 1,000, 2,000 patients and a final analysis will be conducted after completion of the whole data set analysis.
 
At each interim analyses, the proportion of NTRK-rearranged cases will be estimated in order to assess the feasibility of a comparative analysis with matched controls.

M	
Number of Evaluable Patients (estimate): it is anticipated to collect data on 3,700 patients

M	
Sample Size Assumptions/Target Number of Valid Cases (incl. Power and Confidence)
 
No sample size estimate has been calculated. It is assumed that a sample size of 3,700 patients should be sufficient to address the primary objective of this study.

0	
Statistical analyses
 
 
Quantitative variables will be described using mean and standard deviations if the normality assumption is satisfied, else other descriptive statistics (median, range, quartiles) will be reported.
 
Qualitative variables will be described using frequency, percentage and 95% confidence interval (binomial law).
 
Survival endpoints will be analysed using the Kaplan-Meier method. The median survival rates will be reported with a 95% confidence interval. Median follow-up will be calculated using the reverse Kaplan-Meier method.
 

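### The secondary outcome for ORR, DOR and OS is limited to HNSCC, although its objective covers all NTRK-fusion solid tumors; the disease setting is also worded inconsistently

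*Combined protocol and SAP*

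**What the plan says.** **ORR, DOR and OS.** The second bullet of Secondary Study Objectives asks for ORR, DOR and "overall survival (OS) in subjects with locally advanced/unresectable or metastatic solid tumors with NTRK gene fusions". The second bullet of Secondary Outcomes lists the same endpoints, also on first-line therapy, but ends with "overall survival (OS) in subjects with locally advanced/unresectable or metastatic HNSCC with NTRK gene fusions". The bullets before and after it, on fusion frequency and demographics, refer to solid tumors generally.

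Inclusion criterion 2 admits any "solid tumor including but not exclusively: soft tissue sarcoma, BRAF wild type melanoma" and some further named types. HNSCC is not named there, but the list is open, so HNSCC patients are eligible.

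**Disease setting.** The primary objective, inclusion criteria 3 and 4 and the exclusion criterion cover locally advanced, unresectable or metastatic disease. Controls are to be "control subjects with locally advanced/unresectable or metastatic solid tumors, who do not have NTRK fusions". Criteria for selection of evaluable cases includes all patients "who have received at least one systemic anti-cancer therapy for locally advanced/unresectable or metastatic disease" who have PFS information and IHC-tested tumor material.

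Two places differ. Statistical & Analytical Plan and Methodology states the primary PFS comparison as one "between subjects with recurrent/metastatic disease and NTRK fusion versus those without a known NTRK fusion". In Collection of Treatment Information, one item reads "Performance status at the time of first line therapy for treatment of recurrent or metastatic disease", although it sits under the heading "First line systemic treatment for locally advanced/unresectable or metastatic cancer".

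**The concern.** An outcome definition tells the analyst which patients enter the estimate. Here the objective and its outcome name different populations for the same three endpoints, and both texts are current. Followed as written, the outcome would describe one tumor type, and fusion-positive patients with any other tumor would have no listed ORR, DOR or OS outcome. The Rationale says that the natural history of NTRK-rearranged tumors is unknown, and these endpoints are part of describing it. The mismatch also weakens pre-specification: reporting all tumors departs from the listed outcome, and reporting HNSCC alone fails the objective.

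The disease-setting wording raises a smaller doubt. A patient whose first presentation is unresectable, non-metastatic disease is eligible and evaluable, but is neither recurrent nor metastatic. Read literally, the statistical section leaves such fusion cases and their matched controls out of the primary comparison.

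**Working it through.** The contradiction is textual, and the plan has no figure of its own to reproduce: it states that no sample size was calculated and gives no expected number of fusions.

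**Step 1: population for ORR, DOR and OS**

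| Place | Population |
|---|---|
| Study title, primary objective, study population | solid tumors |
| Secondary Study Objectives, bullet 2 (ORR, DOR, OS) | solid tumors with NTRK fusions |
| Secondary Outcomes, bullet 1 (frequency) | solid tumors |
| **Secondary Outcomes, bullet 2 (ORR, DOR, OS)** | **HNSCC with NTRK fusions** |
| Secondary Outcomes, bullet 3 (demographics) | solid tumors with NTRK fusions |

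One line differs from all the others. The abbreviation is not spelled out and occurs only there.

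**Step 2: disease setting**

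| Place | Setting |
|---|---|
| Primary objective; inclusion criteria 3 and 4; exclusion criterion; control selection; evaluable cases | locally advanced, unresectable or metastatic |
| **Statistical & Analytical Plan and Methodology, primary PFS comparison** | **recurrent/metastatic** |
| **Performance-status item** | **recurrent or metastatic** |
| Heading above the performance-status item | locally advanced, unresectable or metastatic |

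The rule for evaluable cases says that all qualifying patients enter the analysis. It therefore conflicts with the narrower wording, and nothing in the plan says which prevails.

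**Step 3: illustrative size of the HNSCC restriction**

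Inputs:
- N = 3,700, from Number of Evaluable Patients.
- Fusion frequency f = 0.2–2%: assumption.
- HNSCC share of fusion cases h = 0–20%: assumption.
- ORR near 40%: assumption.

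Fusion cases, N × f:
- 3,700 × 0.002 = 7.4, about 7
- 3,700 × 0.02 = 74

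HNSCC fusion cases, N × f × h:
- Low f: 7.4 × 0 = 0 to 7.4 × 0.20 = 1.5
- High f: 74 × 0 = 0 to 74 × 0.20 = 14.8, about 15

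The plan calls for 95% binomial confidence intervals for qualitative variables. For x responders among n, the exact (Clopper-Pearson) limits are the 0.025 quantile of Beta(x, n − x + 1) and the 0.975 quantile of Beta(x + 1, n − x).

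| Scenario | Responders / n | Exact 95% CI | Width (points) |
|---|---|---|---|
| High f and h, HNSCC only | 6/15 | 16.3–67.7% | 51.4 |
| High f, all fusion cases | 30/74 | 29.3–52.6% | 23.3 |
| Low f, all fusion cases | 3/7 | 9.9–81.6% | 71.7 |
| Low f, a single HNSCC case | 0/1 | 0–97.5% | 97.5 |

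With no HNSCC case there is nothing to estimate. These counts treat every evaluable patient as assessable for response, whereas the plan requires only PFS information, so the real denominators for ORR could be smaller.

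**The case against.** The strongest reply is that the rest of the plan shows what was meant. The statistical section promises descriptive statistics on treatment outcome without a tumor limit, the evaluable-case rule includes everyone who qualifies, and response, progression and death are collected for all enrolled subjects. A careful analyst would probably treat HNSCC as a slip, and no data would be lost under either reading. This is persuasive about intent, but it does not change the listed outcome. That the word is a slip remains an inference which only the sponsor can confirm. What the reply does establish is that the correction is free. It also supports treating this as something that should be fixed, not as a fatal flaw, since these are descriptive secondary outcomes.

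A second reply is that the case counts rest on outside assumptions and that the intervals show only that fewer cases give wider intervals. That is fair. The HNSCC share in particular has no basis in the documents, and the leading comparison takes the top of both ranges. The figures are an illustration, and the contradiction stands without them.

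Third, the disease-setting point is weaker. The performance-status item takes its scope from its heading, so doubt about whether it is collected is minor. The data collection also records whether disease was locally advanced, unresectable or metastatic at first-line treatment, so the setting will be known for each patient. What remains is that the sentence stating the primary comparison names a different population from the eligibility and evaluability rules.

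**Conclusion.** The concern holds. The ORR, DOR and OS outcome contradicts its paired objective, and that conclusion depends on no assumption. How many cases would drop out cannot be derived from the documents. Under the assumed ranges above, about 0–15 cases would be described instead of about 7–74. At the top of both ranges, with ORR near 40%, the interval would be a little over twice as wide (51.4 / 23.3 = 2.2). At the bottom, with no HNSCC case or only one, ORR could not usefully be estimated.

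The disease-setting mismatch is also real, but secondary. It is a conflict to reconcile, not evidence that locally advanced non-recurrent cases are meant to be excluded.

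**What to change.** Subject to the sponsor confirming its intent:

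- **Secondary Outcomes, bullet 2:** replace HNSCC with solid tumors, so that ORR, DOR and OS cover all evaluable fusion-positive subjects.
- **Statistical & Analytical Plan and Methodology:** describe the primary PFS comparison in the same disease-setting terms as the inclusion criteria, so that fusion cases and matched controls come from the evaluable population.
- **Collection of Treatment Information, performance-status item:** use the disease setting of its own heading.
- **If an HNSCC subset is wanted:** list it as an additional outcome with a reason.

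The cost is three wording corrections before analysis, with no extra data collection and no burden on patients.

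### The tested sample need not pre-date first-line start and its date is not used, so OS in fusion patients is inflated to the extent that patients qualify only through a later sample

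*Combined protocol and SAP*

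**What the plan says.** All references are to the combined protocol and SAP.

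- **Eligibility (Inclusion Criteria, criterion 5):** "Subject has tumor material available for immunoscreening (IHC for NTRK gene fusions". No timing relative to treatment is given.
- **Analysis set (Criteria for selection of evaluable cases):** patients "who have tumor material tested by IHC for NTRK gene fusions", again without a time limit. Criterion 4 and the exclusion criterion mean that patients enter after first-line therapy, so tissue from any point in their course can qualify.
- **Data collected (Visit schedule):** the NTRK fusion block records "Date of sampling and setting (initial diagnosis, locally advanced/unresectable or metastatic disease". The treatment block records first-line start and end dates. The setting categories do not separate before from after first-line start, but the two dates together do.
- **Matching (Statistical & Analytical Plan and Methodology):** "The two groups will be matched with respect to histological subtype, sex, age (+/-5 years), and pathological tumor-node-metastasis (TNM) stage". Sampling time is not a factor.
- **Analysis (same section):** "The Kaplan-Meier method will be employed for the analysis of PFS", and "A nonparametric test, such as the log-rank test, based on the Kaplan-Meier estimator for survival curves, will be employed". A Cox model is optional. The Statistical analyses entry adds "Survival endpoints will be analysed using the Kaplan-Meier method". No delayed entry, landmark or analysis by sampling time is planned.
- **Endpoints:** PFS on first-line therapy is primary and is compared between fusion and matched non-fusion patients. OS is secondary and is specified for fusion patients only. Time zero is not stated.

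**The concern.** A patient whose only testable tissue was taken after first-line start is in the study because he or she lived long enough to give it. Someone with the same disease who died earlier is not. A Kaplan-Meier curve from first-line start treats the interval up to the sample as time at risk, although death in that interval was impossible for anyone in the data. This is immortal time, and it pushes OS upward.

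For PFS the effect depends on why the late sample was taken. If it required the patient to be progression-free, PFS is lengthened. If it required only survival, PFS is lengthened less. If it was a re-biopsy at progression, the PFS event has already happened and the PFS time is not selected upward in the same way.

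At stake are the OS description of fusion patients and, if late sampling differs between groups, the primary PFS comparison. The plan calls an increase in median above 30% clinically relevant whatever the confidence interval width, so a shift in medians alone could be read as a finding.

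**Working it through.** The plan gives no survival figure, event count, late-sample share or calculated sample size, so there is no figure of its own to reproduce. Every input below is an assumption.

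**1. OS, closed form.** Take exponential OS with median 12 months and, for late-only patients, an independent exponential sampling time with median 6 months. Time zero is first-line start. Let *q* be the share of the source population testable only on a late sample, and let x = 2^(−t/12), the true survival at month t.

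- The sampling hazard is twice the death hazard, so P(alive at sampling) = 2/3.
- Late-only patients who are included and survive past t: x − x³/3.
- Observed survival: S(t) = (x − q·x³/3) / (1 − q/3).
- Set S(t) = 0.5, solve for x, then median = −12·log₂(x).

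| q | x | Naive median (months) | Inflation |
|---|---|---|---|
| 0% | 0.5000 | 12.0 | 0% |
| 20% | 0.4738 | 12.9 | 7.8% |
| 30% | 0.4597 | 13.5 | 12.1% |
| 50% | 0.4299 | 14.6 | 21.8% |

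**2. OS and PFS together, by reason for the late sample.** Simulation with true median PFS 6 months, 20% of PFS events being deaths, and median post-progression survival 10 months (true median OS about 16), with no censoring. Late samples arise in one of three ways: (A) at a random time in months 0–12, patient alive; (B) the same, patient still progression-free; (C) 0–3 months after progression, patient alive.

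| Mechanism | Naive PFS, q = 10 / 50 / 100% | Naive OS, q = 10 / 50 / 100% | OS with delayed entry, q = 10 / 50 / 100% |
|---|---|---|---|
| A | 6.1 / 6.7 / 7.6 | 16.4 / 17.8 / 19.7 | 16.1 / 16.1 / 16.2 |
| B | 6.3 / 8.0 / 11.3 | 16.4 / 17.8 / 21.0 | 16.2 / 16.7 / 18.4 |
| C | 6.0 / 6.0 / 6.0 | 16.4 / 17.9 / 20.6 | 15.8 / 14.6 / 10.1 |

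Naive OS is inflated under every mechanism, PFS only under A and B. Delayed entry restores OS under A, leaves it high under B, and over-corrects it under C because entry is then tied to progression.

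**3. Group comparison with no true effect.** 37 fusion patients (1% of 3,700, assumed), 148 controls (1:4, assumed), unstratified two-sided 5% log-rank, 1,500 runs. The Monte Carlo standard error near 5% is √(0.05 × 0.95 / 1,500) = 0.6 percentage points.

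| Late share, fusion vs control | PFS type I error, A / B / C | Chance that the PFS median ratio exceeds 1.3, A / B / C |
|---|---|---|
| 0% vs 0% | 5.9 / 4.9 / 5.1% | 15 / 15 / 15% |
| 50% vs 50% | 5.3 / 5.2 / 4.9% | 17 / 11 / 15% |
| 50% vs 20% | 4.4 / 9.2 / 5.5% | 22 / 38 / 16% |
| 80% vs 20% | 7.5 / 27.1 / 5.6% | 31 / 74 / 16% |

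The comparison is materially disturbed only when shares are unequal and sampling depends on being alive or, above all, progression-free.

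**4. Restricting to early samples.** Keeping only patients not dependent on a late sample gave, at q = 50%, median PFS 5.95–6.0 and OS 16.1 under all three mechanisms. This recovery follows from the simulation assigning late-only status at random. If that status is related to prognosis, the restricted set describes a somewhat different population.

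**The case against.** The strongest reply is that the plan permits late samples only by omission. No passage says they will be used, or how often. An advanced-disease biopsy may be the one taken just before first-line therapy, and criterion 2 asks for "Subject has/had a histologically or cytologically confirmed diagnosis of solid tumor", so many patients should have earlier tissue. This stands: the late share could be small. It does not remove the point, because nothing says the earlier tissue must be the tissue tested.

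Second, a reader might infer that survival is inflated as a matter of fact, or that the primary comparison is biased. The documents support neither. The share is unknown, PFS is unmoved when re-biopsy follows progression, and equal shares leave type I error near 5%. The same IHC screening applies to both groups, controls are matched on histology and stage, and no passage suggests that fusion patients are re-biopsied more often. The 80% vs 20% scenario shows what imbalance could do. It is not a forecast.

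Third, OS is specified in fusion patients only, so a fusion-versus-control ratio of OS medians would describe a comparison the plan does not make. That also stands, and no such ratio is relied on here.

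Fourth, delayed entry, the textbook remedy, can replace upward bias with downward bias, and a fifth matching factor may lose matches in a rare-fusion cohort. Both are right and shape the fix.

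**Conclusion.** The point holds in conditional form. The plan sets no timing rule for the tested sample and does not use the sampling date it collects. OS in fusion patients, measured from first-line start, is inflated to the extent that patients qualify only through a later sample: about 8% to 22% in the median for source-population shares of 20% to 50%, under the exponential model in step 1. The PFS comparison is at risk only if late sampling is both more common in one group and dependent on being alive or progression-free. These sizes rest on assumed survival, sampling times, late shares and numbers of fusion patients. First-line start as time zero is also assumed. This is a low-cost improvement to the analysis and does not show that the primary result will be wrong.

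The rule that first-line therapy must have been received or completed is a separate selection on the patient's course, and it would remain after this change.

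**What to change.** 1. State first-line start as time zero for PFS and OS. From the sampling and first-line start dates, classify each tested sample as on or before, or after, first-line start.
2. Report the share of late samples in fusion patients and in controls.
3. Repeat the primary PFS comparison, and the OS estimate in fusion patients, in those sampled on or before first-line start.
4. Use delayed entry at the sampling date at most as a sensitivity analysis, with the caveat that it over-corrects OS when re-biopsy is triggered by progression (14.6 against a true value of about 16 months at a 50% share). Samples taken after the PFS event add nothing to a delayed-entry PFS analysis.
5. Treat sampling timing as an optional matching factor, used only if matches are not lost.

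No new data are needed. The cost is precision in the restricted analysis. With the assumed 37 fusion patients and a 50% source share, the observed late share under mechanism A is 45%, leaving about 37 × 0.55 ≈ 20.
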